6.2 Definition of Study Epochs and LCIG Treatment Period Reference Variables

The following study epochs have been defined to track each subject's progression from screening through study completion or premature discontinuation.

Epoch Name	Epoch Description
Pre	OMT group: prior to and including the day of randomization. LCIG group: prior to the day of initial device (NJ or PEG-J) placement.
Device Before in Randomized Treatment Period (LCIG group only)	From the date of the first device (NJ or PEG-J) placement procedure up to, but not including, the date of the first LCIG infusion for subjects in the LCIG group during the 26-week randomized treatment period. This Epoch is missing for subjects whose infusion started the same day as initial device placement.
Open in Randomized Treatment Period	OMT group: from the day after randomization through the end of study (date of last visit) during the 26-week randomized treatment period. LCIG group: from the date of the first LCIG infusion through the date of the last LCIG infusion during the 26-week randomized treatment period.
Pre in Extension Period (OMT group entering Extension Period only)	From the day after the last visit during 26-week randomized treatment period up to, but not including date of the first device (NJ or PEG-J) placement.
Device Before in Extension Period (OMT group entering Extension Period only)	From the date of the first device (NJ or PEG-J) placement procedure up to, but not including, the date of the first LCIG infusion.
Open in Extension Period	For subjects in OMT group entering extension period: from the date of the first LCIG infusion through the date of the last LCIG infusion. For subjects in LCIG group entering extension period: from the date after the last LCIG infusion during the 26-week randomized treatment period through the date of the last LCIG infusion during the extension period.
Device After	From the first day after the last LCIG infusion through the date of the final device removal (Note: Subjects who have their last infusion on the same date as their final device removal will progress directly from the Open in Randomized Treatment Period/Open in Extension Period to the Off epoch).
Off	Time period after final device removal for subjects who are discontinuing LCIG treatment. Time period after end of study (date of last visit) for all other subjects.

For subjects randomized to the LCIG group, the date and time of the earliest LCIG tube placement (NJ or PEG-J) recorded on the Device Information eCRF will be considered

the treatment start reference date (REFDT1) and time (DMREFTM). The date of the last LCIG tube removal, or the date of the last LCIG infusion if there is no device removal in the 26-week randomized period will be considered as end of the LCIG 26-week randomized treatment period and the following day will be the post-treatment start reference date (REFEDT1). For LCIG subjects who enter the Extension Period, treatment start reference date in extension period (REFDT2) equals REFEDT1. The date of the last LCIG tube removal or the date the last LCIG infusion if there is no device removal, will be the post-treatment reference date (REFEDT2) of Extension Period.

For subjects in the OMT group, the date after randomization will be considered the treatment start reference date (REFDT1). The date of the final visit during 26-week randomized period will be considered the end of the OMT treatment period and the following day will be the post-treatment start reference date (REFEDT1). For OMT subjects who enter the Extension Period, the date of earliest LCIG tube placement (NJ or PEG-J) recorded on the Device Information eCRF will be considered the treatment start reference date (REFDT2) in Extension period. The date of the last LCIG tube removal, or the date the last LCIG infusion if there is no device removal, will be considered the end of the Extension Period and the following day will be the post-treatment start reference date (REFEDT2).

Study Days during 26-week randomized treatment period will be calculated based on the treatment start reference date (REFDT1). For time points before REFDT1, the Study Day = time point – REFDT1. For time points on or after REFDT1, the Study Day = time point – REFDT1 + 1. Thus, the Study Day is a negative value when the time point of interest is prior to REFDT1 and the Study Day is a positive value when the time point of interest is on or after REFDT1. There is no Study Day 0. The Study Day will be labeled as Rx Day on the data listings. Study Days during Extension Period will be calculated based on the Extension Period start reference date (REFDT2) with the same rule as in 26-week randomized treatment period. For OMT subjects who enter the Extension Period, the study day of Pre in Extension Period will be calculated based on REFDT2.

6.3 Definition of Baseline and Final Observation

Baseline for efficacy, health outcome and safety measures during the 26-week randomized treatment period will be defined as the last non-missing observation that is on or before the day of randomization.

Baseline for safety assessment during the Extension Period is defined as the last non-missing observation that is on or before the day of NJ/PEG-J placement for OMT subjects who enter the Extension Period. For LCIG subjects who enter the Extension Period, baseline of 26-week randomized treatment period will be used as the baseline of Extension Period.

The final visit for efficacy and health outcome measure will be defined as the last non-missing observation that is after the day of randomization for the OMT group during the 26-week randomized treatment period. The final visit for efficacy and health outcome measures for the LCIG group will be defined as the last non-missing observation that is after the date of the first LCIG infusion following PEG-J placement and no more than 1 day after the last LCIG infusion during the 26-week randomized treatment period.

The final observation for safety assessment during the 26-week randomized Treatment Period is defined as:

- For subjects in the OMT group and LCIG subjects who enter the Extension/Transition Period: the last non-missing observation that is after the day of randomization (for the OMT group) or after the initial device placement (for the LCIG group) and during the 26-week randomized treatment period.
- For LCIG subjects who do not enter the Extension/Transition Period: the last non-missing observation that is after the date and time of the first LCIG tube (NJ or PEG-J) placement procedure and no more than 1 day after the final removal of all LCIG tubes during the 26-week randomized treatment period.

The final observation for safety assessment during the Extension/Transition Period is defined as last non-missing observation for OMT/LCIG subjects who enter the Extension/Transition period.

Safety assessments on the date of the initial device placement procedure that do not have a time of assessment or sample collection recorded will be assumed to be post-procedure.

6.4 Analysis by Planned Visit

A midpoint convention will be used to assign all observations to a planned visit based on the Study Day of the observation. If there are multiple observations on the same day, the average will be taken and considered the observation for the day. If more than one observation is assigned to a planned visit, the last observation will be selected and considered the observation for the planned visit.

The following Study Day windows will be used to assign efficacy and health outcome assessments to planned study visits during 26-week randomized treatment period.

Table 1. Analysis Windows for Efficacy Variables

Assessment	Planned Visit	Nominal Study Day	Study Day Range ^a
NMSS, PDSS-2, PDQ-8, PAS, GDS-15, UPDRS and King's PD Pain Scale	Baseline		≤ date of randomization
	Week 6	42	2 – 63
	Week 12	84	64 – 133
	Week 26	182	134 – 222
CGI-C and PGIC	Week 26	182	≥ 2

a. For subjects in LCIG group, all post-baseline assessments must also be after start of LCIG infusion through PEG-J and no more than 1 day after the date of the last LCIG infusion in the 26-week Treatment Period.

The following Study Day windows will be used to assign safety assessments to planned study visits.

Table 2. Analysis Windows for Safety Variables During the 26-Week Treatment Period

Assessment	Planned Visit	Nominal Study Day	Study Day Range ^a
Vital signs and weight	Baseline		≤ date of randomization
	Week 2	14	2 – 28
	Week 6	42	29 – 63
	Week 12	84	64 – 133
	Week 26	182	134 – 186
	Week 27 FU ^b	189	187 – 301
Clinical labs and Electrocardiograms	Baseline		≤ date of randomization
	Week 12	84	2 – 133
	Week 26	182	> 133
Special labs	Baseline		≤ date of randomization
	Week 12	84	2 – 133
	Week 26	182	134 – 231

- a. For subjects in LCIG group, all post-baseline assessments must also be no more than 1 day after the final PEG-J removal for subjects who have their study device removed after their last infusion of Study M12-927 LCIG.
- b. Applicable only to LCIG subjects who will not transition to commercial LCIG and have study device removed.

The following Study Day windows for Extension Period will be used to assign safety assessments to planned study visits for LCIG subject entering Extension Period.

Table 3. Analysis Windows for Safety Variables During the Extension/Transition Period for the LCIG Group

Assessment	Planned Visit	Nominal Study Day	Study Day Range ^a
Vital signs and weight, Clinical labs ^a , Electrocardiograms ^a , and special labs	Baseline ^b		≤ date of last visit in 26-week randomized treatment period for subjects randomized to LCIG group.
	Month 3 ^c	84	1 – 126
	Month 6	168	127 – 200
	Every 3 months following until subjects' transition to commercial LCIG	Previous + 84	Previous lower bound + 84 through previous upper bound + 84

- a. Clinical labs and Electrocardiograms will not be collected during the Transition Period.
- b. Baseline refers the baseline of Extension Period. All days refer to study day in Extension Period. All post-baseline assessments must also be no more than 1 day after the final PEG-J removal for subjects who have their study device removed after their last infusion of Study M12-927 LCIG.
- c. Applicable only to US subjects.

The following Study Day windows for Extension Period will be used to assign safety assessments to planned study visits for OMT subject entering Extension Period.

Table 4. Analysis Windows for Safety Variables During the Extension/Transition Period for the OMT Group

Assessment	Planned Visit	Nominal Study Day	Study Day Range ^a
Vital signs and weight,	Baseline ^a		< date of NJ/PEG-J placement for subjects randomized to OMT group and entering Extension Period
	Week 2	14	2 – 28
	Week 6	42	29 – 63
	Month 3	84	64 – 126
	Month 6	168	127 – 200
	Every 3 months following until subjects' transition to commercial LCIG ^c	Previous + 64	Previous lower bound + 84 through previous upper bound + 84
Clinical labs ^b , Electrocardiograms ^b , and special labs	Baseline ^a		< date of NJ/PEG-J placement for subjects randomized to OMT group and entering Extension Period
	Month 3	84	2 – 126
	Month 6	168	127 – 252
	Every 3 months following until subjects' transition to commercial	Previous + 168	Previous lower bound + 168 through previous upper bound + 168

a. Baseline refers the baseline of Extension Period. All days refer to study day in Extension Period. All post-baseline assessments must also be no more than 1 day after the final PEG-J removal for subjects who have their study device removed after their last infusion of Study M12-927 LCIG.

b. Clinical labs and Electrocardiograms will not be collected during the Transition Period.

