For LCIG subjects who elect to discontinue LCIG and not continue with commercially available product, a V9 will be conducted one week after NJ/PEG-J removal and the follow-up period will be up until 30 days after NJ/PEG-J removal. For LCIG subjects who will transition to commercial product, the SAE/AE follow-up period will be 30 days after conversion to commercial.

Diagnosis and Main Criteria for Inclusion/Exclusion:

Main Inclusion:

1. Subject must have a diagnosis of idiopathic Parkinson's disease according to the United Kingdom Parkinson's Disease Society (UKPDS) Brain Bank Criteria. See Appendix C for UKPDS.
2. Subject demonstrates persistent motor fluctuations in spite of individually optimized treatment.
3. The subject's Parkinson's disease is levodopa-responsive.
4. Subject has had optimal treatment with available anti-PD medication and their motor symptoms are judged inadequately controlled on this optimized treatment. Optimized treatment is defined as the maximum therapeutic effect obtained with pharmacological antiparkinsonian therapies when no further improvement is expected regardless of any additional manipulations of levodopa and/or other antiparkinsonian medication. This will be based on the Investigator's clinical judgment.
5. Subject and/or if applicable, their care-partner must be able to complete the Subject Dosing Diary and must be able to demonstrate the ability to operate, manipulate and care for the infusion pump and tubing.
6. Subject is eligible to transfer to commercial treatment of Duodopa after completing the study based on local country requirements.
7. Subject must have a minimum PDSS-2 total score of 18 at Baseline assessment.*
8. Subject must be able to understand the nature of the study and has had the opportunity to have any questions answered. Prior to the conduct of any study procedures (including any changes occurring in the subject's current therapeutic regimen), the subject, if judged by the PI to have decision making capacity, must have voluntarily signed the Independent Ethics Committees/Institutional Review Board (IEC/IRB) approved Informed Consent. In the absence of subject's ability to provide the informed consent, the informed consent must have been signed by a person who has the legal right to act on behalf of the subject following national laws
9. Male or female subjects at least 30 years of age.

Diagnosis and Main Criteria for Inclusion/Exclusion (Continued):

Main Inclusion (Continued):

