5.3 Efficacy and Safety Assessments/Variables

5.3.1 Efficacy and Safety Measurements Assessed and Flow Chart

After a subject has signed the Informed Consent, the study activities described in [Table 3](#) will be completed. Subject visit days should ideally match the target clinic visit days. Every attempt should be made to bring the subject back on the target visit day. A ± 3 day visit window will be allowed as necessary beginning with the Week 2 visit and a ± 7 day visit window will be allowed as necessary beginning with the Week 6 visit. All attempts should be made to return the subject to the planned visit schedule (e.g., if the subject is two days late for a Study Visit, the scheduling of the next visit date should be based on the original planned visit date). All scheduled visits are calculated based on Study Day 1 (NJ and/ or PEG-J Placement Day for subjects randomized to LCIG and day after randomization for subjects randomized to OMT).

Table 3. Study Activities

Study Day (End of Week)	OMT/LCIG				Titration Visits	OMT/LCIG				LCIG Wk 27 FU ^a	LCIG Transition to Commercial Visits ^b
	V1 Screening Wk -8/-4	V2 Screening Wk -1	V3 Randomization	V4 NJ/PEG-J Placement DI		Wk 2	Wk 6	Wk 12	Wk 17		
Visit Number for OMT/LCIG	V1	V2 ^c (Optional)	V3	V4 ^d	V5	V6	V7		V8	V9	Every 6 and 12 Weeks
Informed Consent ^e	X										
Medical/Neurological/PD History ^f	X										
Concomitant Medication (including anti-PD and NMS medications)	X	X	X	X	X	X	X		X	X	
Anti-PD Medication History	X										
NMS Medication History ^g	X										
MMSE (Mini-Mental State Examination)	X										
Sleep Attacks Questionnaire	X	X	X		X	X	X		X	X	
Physical Examination ^h	X	X	X	X	X	X	X		X	X	
Neurological Exam	X	X	X		X	X	X		X	X	
Dermatological Exam ^h	X								X		
GI Exam ^h	X										
NJ or PEG-J decision	X										
Nasojejunal Tube Placement/Titration ⁱ (Optional)				X							
PEG-J Placement Procedure ^j				X							

Table 3. Study Activities (Continued)

Study Day (End of Week)	OMT/LCIG			LCIG V4 NJ/PEG-J Placement D1	Titration Visits	OMT/LCIG				LCIG	Transition to Commercial Visits ^b	
	V1 Screening Wk -8/-4	V2 Screening Wk -1	V3 Randomization			Wk 2	Wk 6	Wk 12	Wk 17			Wk 22
Radiological Check of Tube Placement ^j				X								
PEG-J Site (Stoma) Check				X ^k	X	X	X		X		X	
Vital Signs ^l /Weight	X		X	X	X	X	X		X		X	X
Height ^m	X											
ECG	X						X		X			
Clinical Labs ⁿ (+ urinalysis) ⁿ	X	X	X ⁿ				X		X			
Urine Drug/Alcohol Screen	X											

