- t. PEG-J removal will be complete 1 week before follow up visit.
- u. At Week 27 follow up visit LCIG cassettes return only.

Note: All applicable clinical, safety, health outcome and cognition assessments will be administered only by individuals qualified by the Sponsor.

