5.4.2 Removal of the PEG-J (LCIG Group Only)

For subjects randomized to LCIG, in case of premature discontinuation of the subject or subject not continuing on commercial treatment, after the PEG-J has been placed, the PEG-J should be removed via endoscopy. The PEG-J should not be removed for 10 to 14 days after placement or until the stoma-tract is formed. Institutional standards for follow-up care after removal of the PEG-J should be followed. The tube must be removed endoscopically by a qualified gastroenterologist proceduralist or surgeon. Follow-up visit with examination should occur 1 week following the PEG-J removal.

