United States subjects in LCIG arm will continue to have study drug dispensation every 4 weeks and will have study visits at 3 and 6 months, or the day prior to transition to commercial if that happens before the scheduled study visits. United States subjects from the OMT arm will undergo the NJ (optional) and PEG-J procedures, titration, plus have visits at 2 weeks, 6 weeks, 3 months and 6 months post NJ or PEG-J, or the day prior to transition to commercial if that happens before the scheduled study visits. Subjects will receive study drug every 4 weeks. The Extension Period will last for a maximum of 6 months to allow for continuity of care while the transition to commercially available drug occurs.

Part 4: Follow-up period. For subjects who elect to discontinue LCIG treatment at any time during the study, the PEG-J tube will be removed following the End of Study activities. A follow-up clinic visit will occur approximately 1 week later. For study subjects who complete participation in the study and will continue to receive LCIG, subjects will return every 6 weeks to return used LCIG cassettes and be dispensed cassettes. Additional visits every 12 weeks from Week 26 will be scheduled to monitor subject safety and allow for drug resupply until the subject transfers to commercial LCIG.

Figure 1. Study Design Schematic (All Countries Except for United States and South Korea)

[figure not shown]
[figure not shown]
[figure not shown]

Figure 2. Study Design Schematic (United States)

Extension Period:

OMT Subjects

LCIG Subjects

[figure not shown]
[figure not shown]
[figure not shown]

Figure 3. Study Design Schematic (South Korea)

[figure not shown]

Extension Period:

OMT Subjects

LCIG Subjects

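### SAP Table 2 has a Week 27 follow-up row for vital signs and weight after tube removal, but its own footnote excludes the visit that row is meant to hold

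*SAP*

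**What the plan says.** SAP Section 6.4 assigns safety values to planned visits by Study Day. In Table 2, the vital-sign and weight block ends with Week 26 (nominal Day 182, range 134-186) and Week 27 FU (nominal Day 189, range 187-301). Two footnotes govern the last row.

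- Footnote b, on the row itself: "Applicable only to LCIG subjects who will not transition to commercial LCIG and have study device removed".
- Footnote a, on the Study Day Range column and so on every row, restricts the LCIG arm: "all post-baseline assessments must also be no more than 1 day after the final PEG-J removal for subjects who have their study device removed". It is worded for removals that follow the last infusion.

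Both documents agree on when the follow-up visit takes place:

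- Protocol Synopsis: "a V9 will be conducted one week after NJ/PEG-J removal".
- Protocol Table 3, footnote t: "PEG-J removal will be complete 1 week before follow up visit".
- Protocol Section 5.4.2: "Follow-up visit with examination should occur 1 week following the PEG-J removal".
- SAP Section 4.2, after describing tube removal: "A follow-up clinic visit will occur approximately 1 week later".

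SAP Section 6.3 applies the same limit to the final safety observation for LCIG subjects who do not continue: "no more than 1 day after the final removal of all LCIG tubes during the 26-week randomized treatment period". No exemption for the Week 27 FU row is stated.

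**The concern.** Footnotes a and b select the same people: LCIG subjects whose tube is taken out. Footnote b opens a row for their post-removal visit. Footnote a then rejects anything later than the day after removal, while the visit is due about a week after removal. A programmer who follows the table literally gets a row that is empty or filled with the wrong values. One who guesses the intent gets something else.

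At stake is the descriptive by-visit record of vital signs and weight after the tube is removed, and of the vitamin panel if it is drawn at that visit. These subjects have stopped LCIG or chosen not to continue it.

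**Working it through.** **1. Reproduce the windows.** The nominal days are 14, 42, 84, 182 and 189, and SAP 6.4 uses a midpoint convention.

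- (14 + 42)/2 = 28
- (42 + 84)/2 = 63
- (84 + 182)/2 = 133
- (182 + 189)/2 = 185.5, which the table rounds up to 186

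These match the printed upper bounds, so the follow-up row starts at Day 187. Its nominal day is 182 + 7 = 189, which fits removal at Week 26 and a visit one week later. The upper bound of 301 is taken as given.

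**2. Apply both conditions.** Let R be the day of final PEG-J removal, with V9 on Day R + 7.

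- Row: 187 ≤ R + 7 ≤ 301, so 180 ≤ R ≤ 294. That is 294 − 180 + 1 = 115 removal days.
- Footnote a: R + 7 ≤ R + 1, which is never true.

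Footnote a keeps 0 of the 115. If the row were exempt, all 115 would be kept.

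**3. Allow the visit tolerance.** Protocol 5.3.1 says "a ± 7 day visit window will be allowed as necessary beginning with the Week 6 visit". With R = 182, V9 may fall on Days 182-196. The days inside the row are 187-196, which are 5 to 14 days after removal, and all are rejected. For any R, the only post-removal values that satisfy both rules are those on the removal day or the day after, which requires R ≥ 186.

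**4. What can fill the row.** A Week 26 visit within tolerance falls on Days 175-189, and Days 187-189 lie in the follow-up row. Protocol 5.1.3 has the tube removed after the end-of-study activities, so a value from such a visit passes footnote a. An on-device value is then labelled Week 27 FU. That subject's Week 26 cell is left empty unless an earlier value falls in 134-186.

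**5. Special labs.** As far as the columns of Protocol Table 3 and SAP Appendix A can be read, these are also scheduled at Week 27. Table 2 gives them only Week 12 (2-133) and Week 26 (134-231). With R = 182, a Day 189 sample is inside 134-231, but 189 > 183, so footnote a drops it. SAP Appendix F has no PCS limits for vitamin B12, vitamin B6, folic acid, methylmalonic acid or homocysteine, so the PCS listing does not show them either.

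**6. Other summaries of these values.** The final observation has the same one-day limit (SAP 6.3). The minimum, maximum and PCS counts are confined to the 26-week randomized treatment period (SAP 10.3 and 10.4), which SAP 6.2 ends at the last tube removal. A PCS weight at V9 would be listed but not counted.

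**7. What Table 2 does not govern.**

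- Adverse events count as treatment-emergent up to 30 days after the last tube removal (SAP 10.2).
- Sleep-attack and C-SSRS responses are taken on or after Day 1, and affirmative subjects are listed (SAP 10.6, 10.8). Those sections also mention the 26-week period, but their listings carry no such limit.
- PCS vital signs and weights are listed whenever they occur in the study (SAP 10.4.3).

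**The case against.** The best defence is that the exclusion is intended. Table 2 is titled for the 26-week treatment period, tube removal ends that period, and an off-treatment value should not enter an on-treatment mean. For the Week 2-26 rows this is right. If the tube is removed on Day 60, V9 falls on Day 67, inside the Week 12 window (64-133), and footnote a properly keeps it out. But the defence leaves the Week 27 FU row with no purpose, and footnote b shows that someone meant to fill it.

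The consequence is also small, and this stands. The OMT group has no V9, so the row could only ever be descriptive and single-arm. Vital signs, weight and special labs are also collected at Week 26 or premature discontinuation, and those values remain usable within the stated windows and limits.

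Three stronger readings are tempting, and the documents do not support them.

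- *The post-removal visit is never analysed.* Step 7 of the working shows otherwise.
- *Weight-loss and polyneuropathy events of special interest are lost.* SAP 10.2.3 builds these from treatment-emergent adverse events, not from Table 2 windows.
- *Follow-up special labs overwrite the Week 26 value.* That would happen only if footnote a were ignored. As written, it prevents it.

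**Conclusion.** The contradiction is real and follows from the text alone. V9 vital signs and weight from PEG-J subjects, taken about 7 days after removal, cannot enter the Week 27 FU by-visit summary. The row can hold only values up to 1 day after removal. If special labs are drawn at Week 27, as the schedules appear to show, no specified by-visit summary presents them.

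Two limits apply. Footnote a names PEG-J removal, so subjects who had only an NJ tube are not clearly covered. The number of subjects affected cannot be derived. A reader might apply an assumed discontinuation rate to the 44 planned per arm, but the 10% in the sample-size section refers to subjects without a post-randomization efficacy assessment, which is a different quantity. Inclusion criterion 6 (eligibility to transfer to commercial product) and the extension period may also make removal uncommon among completers.

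Severity is minor: no efficacy result or between-arm comparison changes.

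**What to change.** In SAP Table 2:

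- Exempt the Week 27 FU row from footnote a.
- Assign the row by visit, as the first assessment after final tube removal, instead of by Days 187-301. Early discontinuers' V9 values are then summarised there, and a late Week 26 visit is not labelled as follow-up.
- Add the same descriptive follow-up row for special labs.
- Keep footnote a for the Week 2-26 rows, so that off-treatment values do not replace on-treatment ones.
- State whether NJ-only subjects come under the removal rule.

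If the sponsor does want post-removal values left out, the alternative is to delete the row and say that they are listed only.

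The cost is SAP wording and one extra descriptive, single-arm table row for special labs. No new data are needed.

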In accordance with the LCIG approved Product Label for countries participating in the study, those subjects randomized to LCIG must discontinue all other anti-PD medications (e.g., dopamine agonists, COMT-inhibitors, amantadine, MAO-B inhibitors, anti-cholinergics, and subcutaneous apomorphine etc.) prior to LCIG initiation on Day 1 (V4); these medications should be tapered off according to the prescribing information and the discretion of the Investigator. With the exception of continuous subcutaneous delivery of apomorphine or levodopa containing formulations, these medications may be restarted if indicated by the subject's individual condition, but not within the first 28 days after LCIG initiation.

For those subjects randomized to LCIG, an optional, temporary nasojejunal (NJ) tube may be used initially to titrate the dose of LCIG. Following the NJ phase, a percutaneous endoscopic gastrostomy with a jejunal tube (PEG-J) will be performed by a gastroenterologist proceduralist. Total time to titration via the NJ and PEG-J should not exceed 14 days. Alternatively, subjects may proceed directly to placement of the permanent PEG-J tube without the NJ phase at the discretion of the principal investigator. If the subject proceeds directly to PEG-J, titration should be completed within 7 days. However, at the PI's discretion additional days of optimization may be made if indicated. Subjects on LCIG will return for study visits at the end of Weeks 2, 6, 12, 26 and 27 following PEG-J placement.

Methodology (Continued):

LCIG Group (Continued):

Subjects and/or caregivers must come into the clinic or pharmacy between V7 (Week 12) and V8 (Week 26) for clinical LCIG return and supply visits so that there is no risk of medication expiring. The drug dispensing visits will occur at Weeks 17 and 22 (\pm 7 days). Other assessments may be completed during these visits if required.

During the treatment phase, medications used to treat specific non-motor symptoms must remain stable for the duration of the study unless medically warranted.

Study Follow-Up

The OMT subjects will not have a follow-up visit (V9).

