4.3 Sample Size

Approximately 88 subjects will be enrolled into the study and randomized in a 1:1 ratio to either optimized medical treatment or LCIG. There are no data on NMSS or PDSS-2 available from randomized trials comparing LCIG and OMT. Interim data from ongoing Phase 3b Study M12-920 showed that the improvement in NMSS total score from baseline to Week 12 is 24.8 in the LCIG group with standard deviation of 24. Results from Zibetti et al (2013) showed that the improvement in PDSS 2 total score after an average of 3.5 months of LCIG treatment was 13.1. The standard deviation was not provided and is estimated to be 12.2 assuming the correlation between baseline and follow-up visits is 0.5.

The significance level for this study is 0.05. For sample size determination, it is assumed that the improvement in the OMT group is 33% of the LCIG group, i.e., the improvement is 8.2 on NMSS total score and 4.3 on PDSS-2 total score, and that the correlation between these 2 measures is 0.5. Simulation showed that a study with 37 subjects per

group will have 90% power to declare statistical significance on at least one of these 2 alternative primary endpoints after multiplicity adjustment using Hochberg procedure. It is further assumed that 10% of randomized subjects in either treatment group will not provide post-randomization efficacy assessment. Additional simulations showed that 44 subjects per group will provide 90% power in the sensitivity analysis using baseline observation carried forward for subjects without post-randomization assessment. Therefore the total planned enrollment is decided to be 88 subjects.

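### The Week 26 vital-sign and weight window in SAP Table 2 closes on Day 186, but the protocol allows the visit through Day 189, so some on-time values have no planned visit

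*SAP*

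**What the plan says.** **Assignment rule.** SAP section 6.4 states: "A midpoint convention will be used to assign all observations to a planned visit based on the Study Day of the observation". For vital signs and weight, Table 2 sets Week 26 (nominal Day 182) at Days 134–186 and Week 27 follow-up (nominal Day 189) at Days 187–301. Footnote b restricts the follow-up row: "Applicable only to LCIG subjects who will not transition to commercial LCIG and have study device removed". Footnote a excludes LCIG values taken more than 1 day after final PEG-J removal.

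**Other Week 26 windows.** Efficacy scales run over Days 134–222 (Table 1). In Table 2, clinical laboratory tests and ECG take anything after Day 133, and special laboratory tests take Days 134–231.

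**Visit timing.** Protocol section 5.3.1 says that "a ± 7 day visit window will be allowed as necessary beginning with the Week 6 visit", and that "All scheduled visits are calculated based on Study Day 1". SAP section 6.2 counts days the same way: "For time points on or after REFDT1, the Study Day = time point – REFDT1 + 1". The protocol synopsis gives OMT subjects no follow-up visit.

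**Use of the window.** SAP section 10.4.1 reports mean change in each vital-sign and weight variable at each planned visit. It compares the arms by ANOVA, with LS means, confidence intervals and P values.

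**The concern.** The Day 186 limit is a midpoint taken against a follow-up visit that only some LCIG subjects have, yet it applies to everyone. An OMT subject, or an LCIG subject who continues on the product, can attend Week 26 within the protocol window and still have weight and blood pressure fall past the cut-off, into a row that by its own footnote does not apply.

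Footnote b can be programmed in two ways: such values are labelled Week 27 follow-up, or they are left without a visit. Under either, they are missing from the Week 26 summary and its between-arm comparison, although they are valid and on time. Other data from the same visit are labelled Week 26, so the tables for one visit would rest on different sets of subjects for no stated reason.

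**Working it through.** **Inputs.** Nominal days 14, 42, 84, 182 and 189, and the Week 26 windows (SAP Tables 1 and 2); ± 7 days counted from Study Day 1 (protocol section 5.3.1); 88 subjects, "randomized in a 1:1 ratio to either optimized medical treatment or LCIG" (SAP section 4.3), so 44 OMT by design.

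**1. Reproduce the plan's limits.** Midpoints of adjacent nominal days:
- (14 + 42)/2 = 28
- (42 + 84)/2 = 63
- (84 + 182)/2 = 133
- (182 + 189)/2 = 185.5, rounded up to 186

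All four upper limits match Table 2. Day 186 therefore comes from the Week 27 visit.

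**2. Permitted Week 26 days.** 182 − 7 = 175 and 182 + 7 = 189, which is 15 days.

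**3. Permitted days outside each Week 26 window.**

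| Data | Window | Permitted days outside |
|---|---|---|
| Vital signs, weight | 134–186 | 187, 188, 189 (3 of 15) |
| Efficacy scales | 134–222 | none |
| Clinical labs, ECG | > 133 | none |
| Special labs | 134–231 | none |

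**4. Share of values affected.** The documents give no distribution of visit days, so this step rests on assumptions. For visits centred on Day 182 with standard deviation s, rounded to whole days and truncated at ± 7:

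share = [Φ(7.5/s) − Φ(4.5/s)] / [Φ(7.5/s) − Φ(−7.5/s)]

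| Assumption | Share | Of 44 OMT subjects |
|---|---|---|
| s = 2 | 1.2% | 0.5 |
| s = 3 | 6.1% | 2.7 |
| s = 4 | 10.6% | 4.7 |
| Uniform over 15 days | 3/15 = 20% | 8.8 |

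The same shares apply to continuing LCIG subjects, whose number is not stated. The counts assume that all 44 attend, so dropout lowers them.

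**5. The Week 27 row itself.** The follow-up visit comes about one week after PEG-J removal (protocol sections 5.1.3 and 5.4.2). Footnote a admits nothing later than 1 day after removal. Read literally, the table excludes the data that its Week 27 row exists to hold.

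**The case against.** The strongest reply is that little depends on this window. Protocol section 5.3.1 tells sites to aim for the target day and to use the window only when needed, so visits should cluster near Day 182. That stands. A reader might infer from 3 days in 15 that one value in five is lost, but that needs visits spread evenly over the window, which is an upper case.

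It also stands that most related outputs are untouched. A Day 187–189 value from an OMT or continuing LCIG subject still counts toward:
- final, minimum and maximum changes (SAP sections 6.3 and 10.4.1);
- BMI shifts (10.4.2);
- potentially clinically significant counts (10.4.3).

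Three stronger readings are tempting, and the documents do not support them:
- *For LCIG subjects who stop, the off-drug follow-up value overwrites the Week 26 value.* A Week 26 value from Days 134–186 sits in a separate window and cannot be replaced. A clash needs a Week 26 visit on Days 187–189, and even then footnote a, read literally, bars the follow-up value.
- *Because weight loss is an adverse event of special interest, that analysis is harmed.* SAP section 10.2.3 defines it by MedDRA queries on adverse event terms, not by windowed weights.
- *Table 6 has the same flaw, since it has no row after Day 182.* Its title limits it to the 26-week period (26 × 7 = 182), and no summary specified in section 10.2 is shown to change because of it.

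None of this explains why weight and blood pressure from a Day 188 visit should be treated differently from the ECG and NMSS of the same visit.

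**Conclusion.** The window is wrong as written, and the consequence is small. On-time vital signs and weight from Days 187–189 in OMT and continuing LCIG subjects are omitted from one output: the Week 26 by-visit mean-change summary and its ANOVA. The number of days (3 of 15) is exact. The share of values is about 1% to 11% under clustered visit timing, and 20% at most under even spread; both rest on assumed visit distributions. Efficacy is unaffected.

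The day count follows protocol section 5.3.1, which starts from Study Day 1. The synopsis instead describes LCIG visits as following PEG-J placement, which could put some visits later in subjects who have an NJ phase; I have not relied on that reading. The protocol at hand is Amendment 4. The SAP cites later country-specific amendments that are not available here, but its section 12.0 reports no change in analysis from Amendment 4.

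**What to change.** 1. **Subjects without a Week 27 follow-up visit** (all OMT subjects, and LCIG subjects who continue): extend the Week 26 vital-sign and weight window to Day 222, as for efficacy. Cap it at the end of the randomized treatment period so that no Extension or Transition values enter. All 15 permitted days are then covered.
2. **LCIG subjects with a Week 27 visit:** separate Week 26 from follow-up by recorded visit or by device-removal date, because no day cut-off can tell a late Week 26 visit from an early follow-up. State this as an exception to the Study Day rule in section 6.4.
3. **Footnote a:** reconcile it with the Week 27 row, for example by exempting that row alone. Make this change together with item 2; lifting the limit alone would let a follow-up value displace a Week 26 value from Days 187–189.

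The cost is a split row, one sentence in section 6.4 and one footnote, plus the matching programming. It needs no new data.
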